4.2 Rationale for Use of PEG IFN- α 2a

Subject compliance with daily interferon α dosing during the prolonged treatment course of therapy is an important factor for achieving clinical benefit. In general, despite the absence of direct comparisons, anti-tumor efficacy appears inferior in those studies where the median interferon α dose delivered is less than 3.6 MIU/m²/day. Similarly, trials performed in Ph-positive CML suggest that an increased AUC, with associated prolonged tumor exposure to the interferon α effect, may be more critical than peak interferon α levels in mediating an anti-leukemic effect. Early discontinuation of interferon α due to toxicity could adversely affect a patient's ability to achieve a response.

If the same clinical benefit can be achieved with a long-acting interferon α , the requirement for multiple injections will be reduced and result in great subject convenience. Given the pharmacokinetics and pharmacodynamics of PEG IFN- α 2a and preliminary assessments of tolerability, PEG IFN- α 2a may widen the therapeutic index for conventional interferon- and offer an improved risk benefit ratio.

4.3 PEG IFN- α 2a

PEGs are amphiphilic polymers of ethylene glycol of varying average molecular weights that can be covalently attached to proteins. Modification of proteins with PEG has resulted in increased serum half-life and reduced immunogenicity for a number of proteins. The properties of pegylated proteins vary with the number of PEG molecules attached per protein molecule and the structure (e.g., linear or branched) and average molecular weight of the PEG polymer. A number of proteins used for patient therapy have now been modified with PEG and evaluated clinically. All of these pegylated proteins have increased half-lives relative to the unmodified proteins. Pegylated proteins are also less immunogenic or nonimmunogenic.

Hoffmann-La Roche has developed a modified form of interferon α -2a, pegylated interferon α -2a (PEG IFN- α 2a, Pegasys), which is chemically modified by the covalent attachment of a 40K branched methoxy polyethylene glycol moiety. Compared with interferon α -2a, PEG-IFN α -2a exhibits sustained absorption, decreased systemic clearance, and an approximately tenfold increase in serum half-life. The biological activity of PEG IFN- α 2a, as measured by 2,5-OAS activity, is similarly prolonged, resulting in a significantly improved pharmacodynamic response compared with interferon α -2a.

Pharmacokinetic and pharmacodynamic data obtained from animals (rat and monkey), phase I studies in healthy volunteers, and phase II and III studies in patients with chronic hepatitis C (CHC) indicate that PEG IFN- α 2a injected once a week has the potential for superior efficacy as compared with interferon α -2a injected three times a week. The adverse effect profile to date is similar to that observed with interferon α -2a. A phase I ascending dose study in patients with renal cell carcinoma has been completed, and the dose being used in the phase II study is 450 μ g. Enrollment in a phase I study in patients with Ph-positive CML has been completed. Although a true MTD was not reached, the dose used in phase III CML study was also 450 μ g.

4.4 Pharmacokinetics of PEG IFN- α 2a

The structure of the PEG moiety directly affects the clinical pharmacology of PEG-IFN α -2a. Specifically, the size and branching of the 40 kDa PEG moiety define the absorption, distribution, and elimination of PEG-IFN α -2a. The pharmacokinetics of PEG-IFN α -2a were studied in healthy subjects and hepatitis C infected patients.

Absorption of PEG-IFN α -2a was sustained, peak serum concentrations were reached 72 to 96 hours after dose administration, and measurable concentrations were seen within 3 to 6 hours of a single dose. Dose proportional increases in AUC and Cmax were seen in patients who received once weekly doses of PEG-IFN α -2a. The absolute bioavailability was 84% and was similar to that seen with IFN α -2a.

The systemic clearance was about 100 mL/h, which was 100-fold lower than that of interferon α -2a. After an

intravenous dose, the terminal half-life was about 60 hours, compared to 3 to 4 hours for standard interferon. The terminal half-life after subcutaneous dosing was longer (about 80 hours, range of 50 to 140 hours). After intravenous dosing, the steady-state volume of distribution was 6 to 14 liters. Based on studies in rats, the drug is distributed to the liver, kidney, and bone marrow as well as being highly concentrated in the blood.

Metabolism is the main clearance mechanism for PEG-IFN α -2a. The kidneys eliminated less than 10% of a dose as the intact PEG-IFN α -2a. The metabolic profile of PEG-IFN α -2a has not been fully characterized. Studies in rats showed that the PEG moiety remained attached as the protein portion was metabolized. The metabolic products of PEG-IFN α -2a (including the PEG moiety attached to the metabolized interferon) were excreted in the urine and bile. In rats, the half-life of the radiolabeled PEG moiety was about 10 days and, thus, within about 40 days the PEG moiety was eliminated from the body.

In patients with CHC, steady-state serum concentrations increased twofold to threefold compared with single-dose values and reached steady state within 5 to 8 weeks of once weekly dose administration. Once steady state was achieved, there was no further accumulation of PEG-IFN α -2a. The peak to trough ratio after 48 weeks of treatment was about 1.5 to 2.0. PEG-IFN α -2a serum concentrations were sustained throughout the 1-week dose interval (168 hours).

4.5 Preclinical Studies with PEG IFN- α 2a

The pharmacologic and immunomodulatory properties of PEG IFN- α 2a relative to those of interferon α -2a were evaluated in both *in vitro* and *in vivo* studies. Since the biological activity of interferon α -2a is species restricted, these studies were performed using cells (bovine, human) or animals (cynomolgus monkeys) in which interferon α -2a is active. The following were the main observations:

- PEG IFN- α 2a retains both the antiviral and antiproliferative activities of unmodified

interferon α -2a, although usually with lower specific activity.

- PEG IFN- α 2a causes less of an immunogenic response in mice than interferon α -2a.
- PEG IFN- α 2a is immunogenic in monkeys, as was anticipated based on the immunogenicity of interferon α -2a in monkeys, but this observation is not considered predictive of the immunogenic potential of PEG IFN- α 2a in humans.

The antiproliferative effects of PEG IFN- α 2a and interferon α -2a were compared in an *in vitro* assay against a series of tumor cell lines, including a CML line (K562), four renal cell carcinoma cell lines (ACHN, A-498, G-402 and Caki-1), and four malignant melanoma cell lines (HS-294-T, A-375, SK-MEL-28 and SK-MEL-3). The data demonstrate that PEG IFN- α 2a maintains antiproliferative activity against this range of human tumor cells. As *in vitro* models cannot account for the pharmacokinetic advantage of PEG IFN- α 2a, the most appropriate assessment would be *in vivo* models, in which this potential benefit of the molecule should be observed. The *in vivo* antitumor effects of PEG IFN- α 2a were evaluated in nude mice bearing human tumor xenografts. Nude mice were injected with tumor cells subcutaneously and tumors were allowed to grow until well-established tumors were present. Treatment with either PEG IFN- α 2a once per week or unmodified interferon α -2a three times per week was administered sc in the opposite flank from the tumor for 4 to 6 weeks. The total weekly doses for PEG IFN- α 2a and interferon α -2a were equivalent. In A-498-bearing nude mice, treatment with 100 g of interferon α -2a three times per week significantly inhibited growth of this tumor compared with untreated controls. In animals treated with 300 μ g (measured as micrograms of interferon α -2a) of PEG IFN- α 2a once per week, PEG IFN- α 2a was more active than interferon α -2a in inhibiting tumor growth and also resulted in tumor regression. In similar experiments using two other renal cell carcinoma cell lines (ACHN and Caki-1), a clear trend toward increased activity of PEG IFN- α 2a over interferon α -2a was found but without the statistical significance seen with A-498. In conclusion, PEG IFN- α 2a shows marked antitumor activity when

administered to nude mice bearing human renal cell carcinoma tumor xenografts.

4.6 Clinical Studies in Healthy Volunteers

PEG IFN- α 2a was administered by subcutaneous injection to 92 healthy volunteers in a phase I double-blind study. Volunteers received single ascending doses of 45, 135 or 270 μ g of PEG IFN- α 2a or 3 MIU (15 μ g) or 18 MIU (90 μ g) of unmodified interferon- α -2a. Results showed that:

- PEG IFN- α 2a had a more favorable pharmacokinetic profile than interferon- α -2a, with decreased clearance and a serum $t_{1/2}$ approximately 10-fold higher.
- PEG IFN- α 2a had an improved pharmacodynamic profile as compared with interferon- α -2a, as measured by a prolonged elevation of 2'5'-oligoadenylate synthetase following single-dose administration.
- The safety and tolerability profiles of PEG IFN- α 2a are similar to those of interferon- α -2a. Neutropenia was more frequent and more marked in PEG IFN- α 2a treated patients, but neutrophil counts recovered in all cases in less than two weeks following drug administration.

4.7 Clinical Studies in Chronic Hepatitis C (CHC)

In a phase II dose-finding study in patients with non-cirrhotic CHC, doses of 45, 90, 180 and 270 μ g of PEG IFN- α 2a once weekly vs 3 MIU interferon- α -2a tiw were evaluated in an ascending dose design. The side effect profile was similar to the adverse events observed with interferon- α -2a, and a dose of 180 μ g has been found acceptable in patients with CHC. At the 270 μ g dose level, 18 of 40 patients required dose modification; however, for patients with CHC a neutrophil count of less than $1.0 \times 10^9 /L$ was considered dose limiting. There were no cases of neutropenic sepsis. A second phase II study has been conducted in 268 cirrhotic patients, and two phase III studies in 1170 patients with CHC have been completed; all studies used Roferon-A as a comparator. In total, data have been generated in 995 hepatitis patients treated with doses of 45 μ g (20 pts), 90

μg (116 pts), 135 μg (215 pts), 180 μg (604 pts), or 270 μg (40 pts) PEG IFN- α 2a. Results showed that:

Results from a Phase II PEG IFN- α 2a ascending dose study confirm the optimal dose of PEG IFN- α 2a for the treatment of CHC to be 180 μg once weekly. Sustained virologic response was 36% in CHC patients without cirrhosis treated with this dose. These results also confirm significant improvements in liver histology for patients treated with either PEG IFN- α 2a or standard interferon α 2a therapy. Pharmacokinetic data from a Phase III multinational study further support the once weekly 180 μg dose of PEG IFN- α 2a for the treatment of CHC.

Results from a Phase II PEG IFN- α 2a pharmacokinetics study confirm the feasibility of similar once-weekly PEG IFN- α 2a dosing in CHC patients with cirrhosis as in healthy volunteers and noncirrhotic hepatitis C patients.

One Phase III PEG IFN- α a study reports virologic sustained responses of 39% in CHC patients without cirrhosis (28% in CHC patients with Genotype 1 infection) when treated with 180 g PEG IFN- α 2a once weekly for 48 weeks. A second Phase III study reports virologic sustained responses of 38% in previously untreated CHC patients with or without cirrhosis treated with either 135 g or 180 g of PEG IFN-2a once weekly for 48 weeks. Sustained virologic response among CHC patients with Genotype 1 infection were 22% and 19% following 180 g and 135 g of PEG IFN- α 2a once weekly for 48 weeks, respectively. Additionally, histologic improvement (defined as 2-point improvement from baseline on post-liver biopsy) occurred in 58% and 48% of patients treated once-weekly with 180 g and 135 g of PEG IFN- α 2a, respectively.

A Phase II/III PEG IFN- α 2a study reports virologic sustained responses of 30% in difficult-to-treat CHC patients with cirrhosis when treated with 180 μg PEG IFN- α 2a once weekly for 48 weeks. Study results also confirm statistically significant improvements in both liver histology and quality of life for patients treated with 180 μg PEG IFN- α 2a when compared with standard interferon α 2a therapy.

The overall frequency and types of adverse events, laboratory abnormalities and drug discontinuations reported during a 48-week course of PEG IFN- α 2a therapy administered once weekly, appear similar to that of a 48-week course of interferon α 2a therapy administered three times a week. Adverse events included fatigue, headache, myalgia, arthralgia, flu-like symptoms, nausea, vomiting, injection site reactions, fever, chills, diarrhea, alopecia, abdominal pain, depression, irritability, insomnia, rigors, dizziness and anorexia. Laboratory abnormalities included neutropenia, thrombocytopenia, abnormal ALT values, hypothyroidism and hyperthyroidism. The incidence of premature withdrawals for adverse events and laboratory abnormalities were similar between the PEG IFN- α 2a dose groups and the interferon α -2a group (approximately 10%).

4.8 Clinical Studies in Renal Cell Carcinoma (RCC)

A phase I/II dose-finding study in advanced or metastatic RCC is fully recruited. Twenty-seven patients had been entered into the phase I portion of this study and dosed in cohorts of six patients with once weekly PEG IFN- α 2a 180 μ g, 270 μ g, 360 μ g, 450 μ g or 540 μ g. Dose limiting toxicities occurring at 540 μ g PEG IFN- α 2a included elevated liver transaminases (1 patient with grade 3 ALT), and fatigue (1 patient with grade 3 fatigue). For this reason, the MTD was determined to be 540 μ g, and the dose chosen to be taken forward into further development is 450 μ g, which has been well tolerated for 3 months or more. Forty additional patients have now been entered into the Phase II portion of the study at the dose of 450 μ g. Three patients have stopped treatment for safety reasons: thrombocytopenia (180 μ g), increased alkaline phosphatase (450 μ g) and GI bleeding/sepsis/seizure, unrelated to treatment (450 μ g). Most patients in the RCC study are tolerating PEG IFN- α 2a well. The types of adverse events have been similar in nature to that of unmodified α -interferons. Adverse event reports are available for 66 patients, and the most frequently occurring (>5%) adverse events include: fatigue, fever, chills, myalgia, nausea, headache, decreased appetite, back pain, dizziness and diarrhea. Changes in laboratory values have generally been mild to

moderate, and are consistent with those expected with the use of alpha interferons. The most important laboratory abnormalities have been elevations in transaminase levels, ranging from minor increases to grade 3 ALT elevations experienced by three patients in the highest dose group tested. These elevations have returned to near baseline either on treatment or after holding a dose. Other laboratory abnormalities include mild to moderate decreases in white cells, neutrophils, lymphocytes, platelets and hemoglobin over the first few weeks of treatment. The only notable instance of hematological toxicity is one patient who experienced neutropenia and developed pneumonia beginning on the third day after the first 180 µg PEG IFN- α 2a injection. Twenty-seven patients have discontinued treatment due to progressive disease. Efficacy assessments are available from the first 27 patients entered in the study. Five of the 27 phase I patients have demonstrated confirmed partial response (18.5%); 12 patients completed the 6-month study and 10 continued treatment in a maintenance phase.

4.9 Prior Clinical Experience with PEG IFN- α 2a in Hematological Diseases

4.9.1 Safety of PEG-IFN - α 2a in the Treatment of Ph-positive CML: Study NO15764

Study NO15764 is a phase I, open-label, nonrandomized, dose-escalation trial of the safety and efficacy of PEG IFN- α 2a in Ph-positive CML. A total of 43 patients received either PEG-IFN α -2a monotherapy (three at 270 µg and six each at 360, 450, 540 or 630 µg) or PEG-IFN α -2a plus cytosine arabinoside (ara-C) combination (six at 450 µg of PEG-IFN α -2a plus 10 mg of ara-C, six at 540 µg of PEG-IFN α -2a plus 10 mg of ara-C, and four at 540 µg of PEG-IFN α -2a plus 20 mg of ara-C). The PEG-IFN α -2a doses were given once weekly. The ara-C doses were given daily. However, for patients in the 540-µg PEG-IFN α -2a plus 20-mg ara-C group, ara-C was given only on 10 days a month.

All patients from all treatment groups had one or more adverse events. The types of adverse events were similar to those seen with α -interferons. The most frequently observed adverse events included fatigue,

headache, rigors, myalgia, decreased appetite, diarrhea, nausea, night sweats, pyrexia, and injection site pain or irritation.

As of November 20, 2001, four patients had died. One patient treated with 450 µg of PEG-IFN - α 2a died of lymphoma. The reasons for the other three deaths (one from the PEG-IFN - α 2a 270-µg group and two from the PEG-IFN - α 2a 630-µg group were not specified. These three deaths occurred 5, 14, and 16 months after treatment ended, and were assumed to had been related to the underlying disease.

A total of 19 serious adverse events were reported in 13 patients. All treatment groups had at least one patient who experienced a serious adverse event. The serious adverse events that were reported included thrombocytopenia, transfusion reaction, gastroenteritis, herpes simplex, viral infection, unevaluable reaction (pregnancy in spouse), pyrexia, device failure, hernia repair, lymphoma, dehydration, diarrhea, liver fatty, blood bilirubin increased, weakness, pleuritic pain, and atherosclerosis. About two-thirds of the serious adverse events were possible, probably, or remotely related to the study drug and usually needed dose reduction or, in a few cases, premature treatment discontinuation. However, most of these serious adverse events resolved without sequelae.

A total of 12 patients withdrew from the study for safety-related reasons. Four of the six patients with 540 µg of PEG-IFN α -2a plus 10 mg of ara-C withdrew, while none of the patients treated with 360 µg of PEG-IFN or 540 µg of PEG-IFN α -2a plus 20 mg of ara-C withdrew for safety related reasons. One or two patients from each of the remaining treatment groups withdrew for safety-related reasons. Of the 12 patients whose treatment was discontinued prematurely for safety reasons, eight patients were withdrawn for adverse events including irritation of the buccal mucosa, lymphoma, mucositis and pruritic rash, fatigue, leg pain, neuropathy, and weakness of the lower extremities; and four patients were withdrawn for laboratory abnormalities including thrombocytopenia, elevated liver enzymes, abnormal liver function tests, and elevated bilirubin.

4.9.2 Safety of PEG-IFN α -2a in the Treatment of Ph-positive CML: Study NO16006

Study NO16006 is a phase III, randomized, open-label, parallel-arm, multicenter trial comparing the efficacy and safety of PEG-IFN α -2a and interferon α -2a in patients with recently diagnosed Ph-positive CML never treated with interferons. Patients have been randomly assigned to receive subcutaneous injection of either 450 μ g of PEG-IFN α -2a once weekly or 9 MIU of interferon α -2a daily (titrated upward from a starting dose of 3 MIU daily) for up to 12 months. Responders to treatment may continue treatment for an additional year. As of November 19, 2001, 71 and 74 patients who received PEG-IFN α -2a and interferon α -2a, respectively, had safety data available.

Eight-five percent and 77% of patients treated with PEG-IFN α -2a and interferon α -2a, respectively, had one or more adverse events. The most common adverse events from both treatment groups were similar to those seen with interferon treatment, such as pyrexia, myalgia, fatigue, rigors, diarrhea, nausea, arthralgia, headache, appetite decreased, and anorexia. Most of these events occurred more frequently in the PEG-IFN α -2a-treated patients than in the interferon α -2a-treated patients.

Two patients from each treatment group have died. CML, aggravated general condition, and thrombotic thrombocytopenic purpura each led to the death of one patient. The reason for the fourth death was not specified.

Fourteen percent of patients treated with PEG-IFN α -2a and 15% of patients treated with interferon α -2a had experienced serious adverse events. About one-third of the reported serious adverse events were possibly, probably, or remotely related to the study drug and required dose reduction or premature treatment discontinuation. However, most of these serious adverse events resolved without sequelae. For the PEG-IFN α -2a-treated patients, serious adverse events were reported more often as general disorders and disorders of blood and the lymphatic system; for the interferon α -2a-treated patients, serious adverse events were reported more often as general disorders,

musculoskeletal, connective tissue, and bone disorders, and cardiac disorders.

Six PEG-IFN α -2a-treated patients (8%) and eight interferon α -2a-treated patients (11%) withdrew because of adverse events or laboratory abnormalities. For the PEG-IFN α -2a treatment group, the safety reasons for patient withdrawal included acute hip pain, thrombocytopenia, very high WBC counts, and low neutrophil and platelet counts and low hemoglobin concentration. For the interferon α -2a treatment group, the safety reasons for patient withdrawal included myalgia, depression, anaphylaxis, femoral head necrosis, and positive chest x-ray and flu-like syndrome.

4.10 Rationale for Dosage Selection

The PEG-IFN dose for this phase II study has been selected based on safety results, the maximum tolerated dose (MTD) determined in the phase I study in patients with Ph-positive CML, in combination with ara-C (Talpaz et al. 2000), and a minimum of 3 months safety data from the patients taking the projected phase III dose. In the phase I RCC study, the MTD was 540 μ g, therefore the dose used in the phase II portion of that study is 450 μ g. Patients in the phase I CML study have shown neutropenia and elevated transaminases starting at 540 μ g, although a formal MTD has not been declared, even at the dose of 630 μ g. When given once weekly, 450 μ g of PEG-IFN α -2a is the dose that is considered to deliver the best balance between immunostimulatory/antiproliferative effect and long-term tolerability. To increase safety of the medication, the starting dose, will be 90 μ g and may be increased to doses of 180 μ g, 270 μ g, 360 μ g, and 450 μ g provided patients do not experience significant side effects.

4.11 Update of study results as of 01/15/2009 and plans

At present the study has accrued 40 patients with PV and 36 patients with ET. Most patients had extensive prior therapies with hydroxurea and anagrelide and all 40 patients with PV had phlebotomies. With a median followup of 24 months on Pegasys therapy, the overall hematologic response rate was 81% with PV (complete

in 78%) and 92% with ET (complete in 86%). These results are the best ever achieved with any form of therapy in PV and ET. In addition, measuring JAK2 V617F mutations, we observed complete molecular responses in 12% of patients and any molecular response in 53% of patients. Side effects were acceptable. At the Pegasys dose of 90 mcg weekly Grade 3 neutropenia was observed in only 8% of patients and other side effects (fatigue, dizziness, depression) in only 4% of patients each. These findings are a true therapeutic breakthrough in the management of PV and ET and have been also reproduced by investigators in France (Kiladjian et.al Blood 112;3065,2008) who reported with Pegasys therapy in 40 patients with PV a CHR in 78%, a complete molecular response in 24%, and a major molecular response in 69%.

Hoffman-LaRoche, the Company, declined to expand the study and provide free drug. Our results suggest this is the best available treatment for these patients. We would like to expand the study and continue therapy with Pegasys commercial preparation. We propose to include up to 100 patients with PV and 100 patients with ET. This will allow a more precise estimate of hematologic and molecular response with long term follow up, a better estimate of long term survival and toxicity profiles, and a treatment of patients on protocol which affords better care by our leukemia experts and allows future analyses of data in a large cohort including an evaluation of prognostic factors that determine molecular response and long term outcome. Our data was presented at ASH 2008 (Quintas-Cardama, Blood 112:653, 2008).

Update September, 2019

Sixteen patients remain on study for a median of 12 years (range 11 - 13). All patients are on a stable dose of pegylated interferon with normal blood counts. None of the patients have experienced drug-related adverse reactions in 9 years. Changes in the protocol reflect standard of care monitoring of patients in long term complete hematologic remission. This study represents the longest follow up of patients with ET or PV treated with pegylated interferon.

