5.0 Patient Eligibility Criteria

5.1 Inclusion Criteria

- Following diagnoses:
 - ET: Patients with PLT $> 600 \times 10^9/l$ documented in the past 12 months; hyperplasia of marrow megakaryocytes in the absence of identifiable cause of thrombocytosis and in the absence of Ph chromosome. Patients with ET and lower PLT will be eligible if attributable to prior ET therapy.
 - PV: Patients should have Hb $\geq 15\text{g/dl}$ (except if patient is having phlebotomies done or is taking hydroxyurea) and documented past diagnosis
- Performance status ≤ 2 (ECOG scale; see Appendix A).
- Age greater than 18 years since disease is extremely rare in younger age group.
- Adequate liver function: total bilirubin of $\leq 2.0\text{ mg/dl}$ (except for patients with Gilbert's Syndrome) and AST (SGOT) or ALT (SGPT) $< 3 \times \text{ULN}$ (or $< 5 \times \text{ULN}$ if considered due to tumor), and renal function (serum creatinine $\leq 2.0\text{ mg/dl}$)
- Signed informed consent indicating that patients are aware of the investigational nature of this study in keeping with the policies of the M.D. Anderson Cancer Center. The only acceptable consent form is the one approved by the M.D. Anderson Cancer Center IRB.
- Willingness and ability to comply with the requirements of the protocol for the duration of the study.
- Patients must have been off chemotherapy for 1 week prior to beginning Pegasys and have recovered from the toxic effects of that therapy. Patients may have received hydroxyurea or anagrelide immediately before study entry, and may continue into therapy if treating physician determines that this is in the best interest of the patient.

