8.1 Monitoring of Patients on Study

Patient will be given instructions and the M.D. Anderson contact name (principal investigator/MD Anderson Leukemia staff treating physician), phone, and fax numbers. The patient's local doctor will be identified, contacted, and the protocol details discussed.

All therapy will be given under the care of the patient's local doctor and MD Anderson Leukemia staff treating physician. The patient's local doctor should contact the MD Anderson Leukemia staff treating physician before any dose modifications are considered, and the modifications should be initiated only by the MD Anderson Leukemia staff treating physician or principal investigator, and complications will be dictated at each follow-up visit.

From past experience, it is recognized that treatment provided in collaboration with patient's local doctor outside MD Anderson may occasionally result in some difficulties such as 1) not performing tests as required, 2) not sending results of tests or updates of patient courses, 3) and not informing on toxicities and hospitalizations. This type of therapy is already broadly practiced in the community. Therefore: 1) we will discuss with the patient's local doctor about the protocol and doses, 2) we will make significant efforts (contact at least twice and document) to retrieve the information (tests, toxicities, hospitalizations), and 3) we will document all the information on follow-up visits. Since information may still be missing in one or more components in some patients (e.g. missing CBC or SMA-7, missing drug administration record), these types of difficulties will be collected and documented in the patient's medical record. This will reflect the oncology community practice of the program.

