9.0 Criteria for Response and Toxicity

9.1 Criteria for Response

9.1.1 ET

CR = Reduction of PLT to $<440 \times 10^9/l$ and disappearance of thromboembolic events, without the use of anagrelide or hydroxyurea

PR = Reduction of PLT by 50% but still $>440 \times 10^9/l$ or reduction of thromboembolic events by 50%, without the use of anagrelide or hydroxyurea

9.1.2 PV

CR = Normalization of Hb ($< 15.0 \text{ g/dl}$), no phlebotomies needed, and disappearance of splenomegaly by palpation, without the use of anagrelide or hydroxyurea

PR = A 50% reduction in phlebotomies rate or splenomegaly reduced by 50% by palpation, without the use of anagrelide or hydroxyurea

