11.2 Update of statistical considerations as of 1/15/2009

Experience in 76 patients has shown very high response rates of 78% to 86% in ET and PV. This expansion of the study is to provide patients with the best available treatment, Pegasys, at an optimal dose schedule, in the context of a study using the commercial drug. Up to 100 patients with ET and 100 patients with PV will be treated. This will allow for 1) a large scale capture of more precise response data (hematologic, molecular), 2) detailed analysis of side effects, 3) evaluation of longer term prognosis and survival, and 4) analysis of potential prognostic factors associated with molecular response. Such analyses will be conducted using standard analytical methods.

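### Does the 81% PV response rate, which no count out of 40 can give, show that patients were left out of the primary response rate?

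*Combined protocol and SAP*

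**What the plan says.** Section 4.11, the update dated January 2009, gives the accrual: "At present the study has accrued 40 patients with PV and 36 patients with ET". It then gives the PV result: "With a median followup of 24 months on Pegasys therapy, the overall hematologic response rate was 81% with PV", with complete response in 78%. For ET it gives 92% overall and 86% complete. No numerators or denominators are printed.

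Section 11.2 restates the result: "Experience in 76 patients has shown very high response rates of 78% to 86% in ET and PV". These two figures are the complete response rates of section 4.11. The first aim it lists for the expansion is "a large scale capture of more precise response data (hematologic, molecular", and on method it says "Such analyses will be conducted using standard analytical methods".

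Three other sections bear on who is counted:

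- Section 5.1 on prior and continuing treatment: "Patients may have received hydroxyurea or anagrelide immediately before study entry, and may continue into therapy", if the treating physician judges this best for the patient.
- Section 9.1 attaches the same condition to every response category; for ET complete response it reads "disappearance of thromboembolic events, without the use of anagrelide or hydroxyurea".
- Section 8.1 on data from local doctors: "Since information may still be missing in one or more components in some patients (e.g. missing CBC or SMA-7". It also commits the team to at least two documented contacts to retrieve what is missing.

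Section 11.1 sets the efficacy criterion, a response rate of 35% or more in each disease.

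**The concern.** A proportion that cannot arise from the stated number of patients often means that a different number was used. The ET rates fit all 36 accrued patients and the PV overall rate does not fit 40. One could infer that some PV patients were dropped as not evaluable while no ET patient was.

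The plan has no sentence that would rule this out. Section 11 names no analysis set and does not say how to count a patient who withdraws, lacks blood counts, or stays on hydroxyurea or anagrelide.

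Efficacy is the primary objective, and the expansion to 100 patients per disease is meant to sharpen the response estimate. If patients with poorer outcomes were left out of the denominator, the rate would be too high. More patients would narrow the interval without removing that bias.

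**Working it through.** **Inputs.** Section 4.11: 40 PV and 36 ET patients; PV 81% overall and 78% complete; ET 92% overall and 86% complete. Section 11.1: target 35%.

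**Step 1: reproduce each printed rate on full accrual (100 × k/n, rounded to a whole percent).**

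| Rate | Printed | Nearest count | Result |
|---|---|---|---|
| PV complete | 78% | 31/40 | 77.5%, fits |
| ET overall | 92% | 33/36 | 91.7%, fits |
| ET complete | 86% | 31/36 | 86.1%, fits |
| PV overall | 81% | 32/40 or 33/40 | 80.0% or 82.5%, no fit |

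Truncating or rounding up does not rescue the last row. Three of the four rates reproduce and one does not.

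**Step 2: can 81% arise with nobody left out?** Yes, if rounded parts were added. Complete response is 31/40 = 77.5%, shown as 78%. One partial response is 1/40 = 2.5%, rounded to 3%. Then 78 + 3 = 81, while the true overall rate is (31 + 1)/40 = 80.0%. The error is one percentage point.

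**Step 3: can it arise from a smaller denominator?** Yes. The denominators up to 40 that give both 81% and 78% are 37 (30 and 29 responders), 36 (29 and 28), 32 (26 and 25) and 27 (22 and 21). The printed figures cannot separate steps 2 and 3, or exclude a plain misprint.

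**Step 4: does the answer matter for the efficacy criterion?** Put each candidate over all 40 and, as the least favourable assumption, count every omitted patient as a non-responder. Intervals are exact (Clopper-Pearson).

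| Explanation | PV overall over 40 | 95% interval |
|---|---|---|
| 37 counted, 3 omitted all responders | 33/40 = 82.5% | 67.2 to 92.7 |
| Rounded parts added | 32/40 = 80.0% | 64.4 to 90.9 |
| 37 counted | 30/40 = 75.0% | 58.8 to 87.3 |
| 36 counted | 29/40 = 72.5% | 56.1 to 85.4 |
| 32 counted | 26/40 = 65.0% | 48.3 to 79.4 |
| 27 counted | 22/40 = 55.0% | 38.5 to 70.7 |

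Every lower limit exceeds 35%. The last row requires 13 of 40 patients to have been left out and none of them to have responded; nothing in the documents suggests this.

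**Step 5: does the missing denominator rule leave patients unclassified?** Take the three groups in turn.

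- Still on hydroxyurea or anagrelide: section 9.1 makes freedom from both drugs part of complete and partial response in both diseases. Such a patient meets neither category and is a non-responder. No text removes the patient from the denominator.
- Missing counts: section 8.1 commits to retrieval as well as documentation, and section 8.0 schedules repeated visits and blood counts. One missing count does not make response unassessable.
- Withdrawn: section 10.0 says that every effort will be made to complete and report the observations. In the pilot study described in section 3.2, two of eleven patients stopped at 4 and 5 months, and complete response at 4 months was still reported as 11 of 11.

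No section prescribes an evaluable-only analysis.

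**The case for a change.** The strongest case for a change is that section 11 should not leave the denominator of the primary endpoint to inference. Two analysts could, in principle, report different rates from the same data, and one sentence would prevent it at almost no cost. Bias from a selective denominator also does not shrink with sample size. With 37 patients counted and the other 3 non-responders, PV overall response falls from 30/37 = 81.1% to 30/40 = 75.0%, about 6 points.

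What stands is that 81% is not a valid proportion of 40, that section 11.2 calls complete response rates simply response rates, and that an explicit analysis-set sentence would have been tidier.

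The 6-point figure does not stand as evidence. It assumes both that patients were omitted and that none of them responded, and the documents give no counts for either. Carrying the 20% adverse dropout rate for PV from section 3.2 forward as a share excluded has the same weakness, since stopping for toxicity does not make response unassessable. Nor can the PV rates be replaced by 75.0% and 72.5%: under the rounding explanation the overall rate is 80.0%, and if three omitted patients had all responded it would be 82.5%.

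**Conclusion.** The concern does not call for a change to the plan. The 81% is at least a clerical slip in a dated progress summary. It may be one point too high, or it may rest on a smaller unstated denominator, and the documents cannot settle which. Section 11 does not repeat it, and it sets no stopping boundary, threshold or sample size. Correcting it would alter nothing that the trial does or concludes: under every denominator that fits, and with all omitted patients taken as non-responders, the lower 95% limit for PV overall response is at least 38.5%, above the 35% target.

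The absent denominator sentence is missing detail that analysts fill sensibly. Counting all treated patients is the natural reading of a single-arm response rate, section 9.1 already classifies patients still on hydroxyurea or anagrelide, and sections 8.1 and 10.0 commit to recovering data.

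This conclusion rests on two assumptions: that the 2009 rates come from at most the 40 PV and 36 ET patients stated, and that no appendix absent from the supplied text prescribes an evaluable-only analysis.
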